APPENDIX J: Pre-Registered Patients Outcome Analysis

Table of Contents

1. Introduction.....	89
2. Objectives.....	89
3. Patient Selection	90
4. Study Parameters and Data Management.....	90
5. Statistical Analysis	90

1. Introduction

The primary and secondary endpoints of PROSPECT are focused on the cohort of patients found to have unifocal cancer on MRI and low risk pathology, therefore treated without radiotherapy. There are an additional 242 patients who agreed to have MRI but were not found to be eligible to omit radiotherapy according to the protocol. The information from these patients' screening MRI has been used in directing their care. If the primary analysis of PROSPECT shows a sufficiently low risk of local recurrence without radiotherapy in this select group, it will argue that patients with early apparently unifocal breast cancer should undergo MRI with view to selective use of radiotherapy. The impact of MRI on those within the cohort who turn out to be unsuitable for selective radiotherapy will be an important aspect of the consideration as to whether to undergo preoperative MRI.

Collecting follow up data on these patients will help document the full impact of the MRI before initial surgery. Data collection will be similar to the main study: details of surgery and adjuvant therapy; follow up details including dates and timing of imaging; and details of any breast cancer events. The intent is to determine the status of all patients at the scheduled times of initial and subsequent analyses of the main study and as defined by the protocol – namely May 2021 (when the 100th patient has reached 5 years of follow up) and May 2026 (when the 100th patient has reached 10 years of follow up).

We propose to contact the 242 patients who agreed to have MRI but were not found to be eligible to omit radiotherapy to ask them to consent to follow up in order to determine their outcomes and to allow assessment of the overall impact of the 'PROSPECT model of care': MRI for all and selective use of radiotherapy.

2. Objectives

- To determine the outcomes for patients who had MRI but were found to be ineligible for the main PROSPECT study.
- To assess the overall impact of MRI and selective use of radiotherapy across the entire group of patients screened for PROSPECT.

3. Patient Selection

Patients who have had MRI and subsequently been deemed ineligible for the main study will be asked to consent for further research on descriptive analysis. Verbal consent will be accepted from patients who are unable to complete written consent. The consent discussion will be documented in the medical record and on the consent form.

Those patients who refuse to complete the consent and decline participation outright, will not have additional information included, beyond the details collected as part of the screening aspect of the study to which they have already consented. They will be reported as 'refused consent' for all other additional information.

A request to waive consent will be submitted to HREC for those patients who have died in the intervening time, those who are unable to provide informed consent due to mental deterioration and for those who are unable to be contacted. For these patients, information available within the medical records will be used in the study.

4. Study Parameters and Data Management

The following information will be collected for up to 10 years from pre-registration:

- Treatment as per main study patients, but will also include radiation therapy treatment
- Endocrine therapy
- Recurrence; collect on-going data (as per current patients).

Data submission will occur in time for the primary and secondary analyses (see Section 11):

- At primary analysis: Data will be collated and submitted once in preparation for the primary analysis and will include all required data from the intervening period of pre-registration up to and including the primary analysis data cut off.
- At any secondary analysis: Data will be collated and submitted once in preparation for any subsequent secondary analysis and will include all required data from the intervening period from last data submission up to and including the secondary analysis data cut off.

5. Statistical Analysis

Descriptive analysis of the outcomes of the patients in this substudy will be analysed as per Section 11. This will be a separate analysis from the main PROSPECT cohort.

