12.3 Informed Consent

The Participant Information Sheet and Consent Forms (screening and main) must be reviewed and approved by BCT and the approving HREC prior to trial initiation. For multi-centre ethics submissions, the lead HREC will review the template Participant Information Sheet and Consent Forms. Any subsequent changes to these documents (other than local site identifiers) must be approved by BCT prior to submission to the HREC. Template Participant Information and Consent Forms are provided in Appendix A.

Informed consent from each patient must be obtained prior to initiating any trial procedures in accordance with the International Conference on Harmonisation for Good Clinical Practice (ICH-GCP). All potential trial participants will be given a copy of the HREC approved Participant Information Sheet and Consent Forms to read and discuss with family, GP etc. The investigator will explain all aspects of the trial in lay language and answer all questions regarding the trial.

If the patient decides to participate in the trial, she will be asked to sign the Informed Consent documents (screening initially and if eligible following screening then the

main). One copy of the Participant Information Sheet and signed Informed Consent must be given to the patient to keep and one copy must be retained in the institutional Investigator File. The completed and signed Informed Consent documents for all patients at the institution must be available in the case of data audits. Patients who refuse to participate or who withdraw from the trial will be treated without prejudice.

Regarding the substudy of outcomes of the patients who underwent MRI but were deemed unsuitable for inclusion in the main study, patients will be asked to sign the relevant Informed Consent document. Those patients who refuse consent, or decline to complete the consent, will not have additional information included, beyond the details collected as part of the screening aspect of the study to which they have already consented. They will be reported as 'refused consent' for this additional information.

A request to waive consent will be submitted to HREC for those patients who have died in the intervening time, those who are unable to provide informed consent due to mental deterioration and for those who are unable to be contacted. For these patients, information available within the medical records will be used in the study.

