APPENDIX K: PROSPECT Sequencing Substudy

Table of Contents

1. Introduction.....	91
2. Objectives.....	91
3. Procedures.....	92
4. Study Parameters and Data Management.....	92
5. Outcomes and significance	92

1. Introduction

The Post-operative Radiotherapy Omission in Selected Patients with Early breast Cancer Trial (PROSPECT) clinical trial has used breast MRI in combination with pathological features, to prospectively identify women who might safely avoid radiotherapy due to a low risk of local recurrence.

The study has screened 443 patients over approximately 8 years of recruitment and allocated 201 patients to the no-radiation (“main study”) arm. After a median follow up of 60 months (range: 24-120), primary analysis of the 201 patients has revealed a 1% rate of ipsilateral local recurrence, with a total of 3 ipsilateral events observed at 4.5, 6.5 and 7.5 years. In addition, there was one regional recurrence and one regional/distant recurrence. The latter recurrence exhibited a different tumour morphology (lobular phenotype) compared to the index cancer (which had a ductal phenotype). There have been a similar number of contralateral events. For the subset of screened patients who were excluded from the main study (and therefore received radiotherapy), so far there have been 3 ipsilateral events in approximately 230 patients.

These findings – a similar ipsilateral and the contralateral event rate, late local recurrence, and discordant morphology between the distant recurrence and the index lesion – suggest that some of these recurrences could represent independent tumours, rather than true tumour recurrences. This is an important distinction, as adjuvant therapy given at the time of initial treatment is less likely to be effective in reducing the incidence of independent new events.

We propose to conduct sequencing of the index and subsequent lesions to determine whether they are true recurrences or whether they are independent lesions.

We also propose to analyse the index lesion where there has been a subsequent event using the PAM50 assay, to determine whether it may identify those at high risk of recurrence.

2. Objectives

Objective 1.1: Next Generation Sequencing of primary and recurrent tumours to determine whether ipsilateral local or regional and distant events are true recurrences or independent of the primary tumour

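### Appendix J brings in patients who died by waiver but lets living patients refuse, so mortality in the 242 unregistered patients is liable to be overstated; its refuser definition also conflicts with Section 12.3

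*Protocol*

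**What the plan says.** Appendix J, section 1, defines the group: "There are an additional 242 patients who agreed to have MRI but were not found to be eligible to omit radiotherapy according to the protocol". It intends to establish the status of all of them at the main study's analysis dates, May 2021 and May 2026.

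Appendix J, section 3, sets three routes:

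- **Waiver.** "A request to waive consent will be submitted to HREC for those patients who have died in the intervening time". The same request covers "those who are unable to provide informed consent due to mental deterioration and for those who are unable to be contacted". Their data come from existing files: "For these patients, information available within the medical records will be used in the study".
- **Consent.** Other patients are asked to agree. "Verbal consent will be accepted from patients who are unable to complete written consent".
- **Refusal.** Refusers contribute nothing beyond the screening data already consented to, and are reported as having refused. Here a refuser is someone who will not complete the consent *and* turns participation down altogether.

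Section 12.3 covers the same substudy and the same waiver groups. It says that "patients will be asked to sign the relevant Informed Consent document", and its refuser rule is joined by *or*: "Those patients who refuse consent, or decline to complete the consent, will not have additional information included".

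Appendix J, section 5, sends the analysis to Section 11. Section 11.2.3 lists breast-cancer specific and overall survival at 5 and 10 years, described with Kaplan-Meier curves.

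**The concern.** Follow-up runs from pre-registration, but the decision that lets a patient in is made later, when some patients have already died. A patient who has died cannot refuse; a living, reachable patient can. Losses to refusal therefore fall only on patients alive at contact, which removes survivors from the denominator and leaves the deaths in the numerator. A recurrence that proved fatal before contact is likewise more likely to be kept than one in a patient still alive.

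The refuser definition decides whose records may be used, so a conflict between two sections is a protocol and ethics matter. Sites following different sections would drop different patients.

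What is at stake is Appendix J's second objective, the overall impact of MRI with selective radiotherapy across everyone screened. The 242 are 242/443 = 55% of that cohort.

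**Working it through.** **Reproducing the plan's figure.** Appendix K states: "The study has screened 443 patients over approximately 8 years of recruitment and allocated 201 patients to the no-radiation" arm. 443 − 201 = 242, which matches Appendix J exactly.

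**Inputs not in the protocol.** It gives no count of deaths, refusals or failed contacts for this group. Deaths before contact (D) and the share of living patients who refuse are assumed below and shown as a range.

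**Formula.** Let N = 242 and R = number of living refusers. Waived patients stay in, so only refusers leave.

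- True mortality at contact: D/N
- Mortality among those included: D/(N − R)
- Ratio: N/(N − R)

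R is the assumed share of the N − D living patients, rounded.

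| D (assumed) | True D/N | 5% refuse | 10% refuse | 20% refuse | 30% refuse |
|---|---|---|---|---|---|
| 5 | 2.07% | 5/230 = 2.17% | 5/218 = 2.29% | 5/195 = 2.56% | 5/171 = 2.92% |
| 12 | 4.96% | 12/230 = 5.22% | 12/219 = 5.48% | 12/196 = 6.12% | 12/173 = 6.94% |
| 24 | 9.92% | 24/231 = 10.39% | 24/220 = 10.91% | 24/198 = 12.12% | 24/177 = 13.56% |

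The ratio is about 1.05 at 5% refusal, 1.10–1.11 at 10%, 1.22–1.24 at 20% and 1.37–1.41 at 30%.

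**The only related figure in the protocol.** Appendix K speaks of approximately 230 excluded patients. If the whole gap to 242 were refusals (the text does not say so), R = 12 and the ratio is 242/230 = 1.05.

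**Missed deaths.** If records miss a share m of deaths and those patients are counted as alive, included mortality is D(1 − m)/(N − R). This equals D/N when m = R/N. With D = 12, 10% refusal (R = 23) is offset by 12 × 23/242 = 1.1 missed deaths, and 20% (R = 46) by 12 × 46/242 = 2.3.

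**Later analyses.** Refusers' deaths after contact are lost along with their denominators, so the bias is diluted. Assume 10% total mortality, half of it after contact, and 30% refusal among those alive at contact. Included mortality is (0.05 + 0.05 × 0.70)/(1 − 0.95 × 0.30) = 0.085/0.715 = 11.9%. If all deaths came before contact it would be 0.10/(0.10 + 0.90 × 0.70) = 13.7%. The excess roughly halves.

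**Waiver declined.** Patients who died before contact then contribute nothing after screening, and mortality is understated.

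**The two refuser rules, side by side.**

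| Reachable, capable patient | Section 12.3 | Appendix J |
|---|---|---|
| Declines outright and does not complete the form | Refuser | Refuser |
| Does not complete the form but never declines outright | Refuser | Not a refuser, not a consenter, not in a waiver group |

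The second row is the contradiction. It changes R; it does not create the dependence on vital status.

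**The case against.** The strongest reply is that nothing shows mortality will in fact be overstated. The waiver is only requested. Waived patients are followed through records alone, and those who cannot be contacted may have died elsewhere, so it cannot be said that every death is captured. One or two missed deaths could cancel the effect. No refusal rate is given, and the one related figure points to about 1.05 at most. Appendix J's own data list names treatment, endocrine therapy and recurrence, not death. The substudy is descriptive and kept separate from the main cohort, refusers are to be reported, and denominator rules often belong in a statistical analysis plan.

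Most of this stands and limits the size and certainty. It does not remove the point. Survival does enter, through the reference to Section 11 and the stated intent to establish every patient's status. Who is included is fixed in the protocol's consent rules and depends on vital status whether the waiver is granted or declined. Using a refusal date needs ethics agreement, so it cannot be left wholly to an analysis plan.

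A reader might also infer that the verbal-consent provision contradicts Section 12.3, so that a woman who agrees verbally but never signs is in under one section and out under the other. The text does not support that. Verbal consent is limited to patients unable to complete the written form, and being unable is not declining.

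**Conclusion.** Mortality in the 242 is liable to be overstated if the waiver is granted and living patients refuse, and understated if the waiver is declined. For deaths before contact the factor is about 1.05 at 5% refusal and about 1.2 at 20%. With 12 assumed deaths that is an excess of about 0.3 and 1.2 percentage points. These figures assume that records capture all deaths.

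A reader might conclude that mortality *is* overstated, or by as much as 40%. The protocol supports neither: the direction depends on the waiver, and the upper figure needs 30% refusal, which nothing in the document suggests. Nor does the wording conflict cause the bias; it is a separate contradiction over who counts as a refuser.

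The main study's primary endpoint is untouched. This is a minor point with a cheap improvement available.

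**What to change.** 1. Reconcile Section 12.3 and Appendix J, section 3, into one refuser rule that also classifies the reachable patient who neither completes the form nor declines outright.
2. For overall and breast-cancer specific survival, keep refusers in the denominator from pre-registration, censored alive at the refusal date, subject to ethics agreement. For deaths before contact this restores D/242, for example 12/242 = 4.96% instead of 12/196 = 6.12%.
3. Report the number of refusers beside the survival results, so that the size of the selection is visible.
4. For recurrence, add a sensitivity analysis beside the unweighted result. Weight living consenters by living patients approached divided by living patients consenting, and give waived patients weight 1. State the assumption that refusal is unrelated to recurrence among the living.

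The cost is wording in two sections, ethics agreement to use the refusal date, one weighted analysis, and slightly wider intervals for the weighted result.

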APPENDIX K: PROSPECT Sequencing Substudy

Table of Contents

1. Introduction.....	91
2. Objectives.....	91
3. Procedures.....	92
4. Study Parameters and Data Management.....	92
5. Outcomes and significance	92

1. Introduction

The Post-operative Radiotherapy Omission in Selected Patients with Early breast Cancer Trial (PROSPECT) clinical trial has used breast MRI in combination with pathological features, to prospectively identify women who might safely avoid radiotherapy due to a low risk of local recurrence.

The study has screened 443 patients over approximately 8 years of recruitment and allocated 201 patients to the no-radiation (“main study”) arm. After a median follow up of 60 months (range: 24-120), primary analysis of the 201 patients has revealed a 1% rate of ipsilateral local recurrence, with a total of 3 ipsilateral events observed at 4.5, 6.5 and 7.5 years. In addition, there was one regional recurrence and one regional/distant recurrence. The latter recurrence exhibited a different tumour morphology (lobular phenotype) compared to the index cancer (which had a ductal phenotype). There have been a similar number of contralateral events. For the subset of screened patients who were excluded from the main study (and therefore received radiotherapy), so far there have been 3 ipsilateral events in approximately 230 patients.

These findings – a similar ipsilateral and the contralateral event rate, late local recurrence, and discordant morphology between the distant recurrence and the index lesion – suggest that some of these recurrences could represent independent tumours, rather than true tumour recurrences. This is an important distinction, as adjuvant therapy given at the time of initial treatment is less likely to be effective in reducing the incidence of independent new events.

We propose to conduct sequencing of the index and subsequent lesions to determine whether they are true recurrences or whether they are independent lesions.

We also propose to analyse the index lesion where there has been a subsequent event using the PAM50 assay, to determine whether it may identify those at high risk of recurrence.

2. Objectives

Objective 1.1: Next Generation Sequencing of primary and recurrent tumours to determine whether ipsilateral local or regional and distant events are true recurrences or independent of the primary tumour

Objective 1.2: Exploratory analysis of primary tumour mRNA via PAM50 to determine the nature of the primary that was associated with subsequent events

3. Procedures

To address these questions, we propose to undertake next generation sequencing of the index cancer and matched subsequent events to determine whether these represent true recurrences or whether the metachronous cancers are due to an unrelated second cancer. Germline DNA will also be obtained and sequenced to facilitate the evaluation of the tumours. Tumour mRNA profiling (PAM50) will also be conducted.

All patients have provided consent for use of tissue samples for Ethics-approved research, either as part of consent for the main PROSPECT study or via separate “Tissue Bank Consent”. For all future patients in whom there is an eligible event, a request will be made for consent to undertake these analyses in the future.

Samples of the index and matched subsequent lesions and paired blood or buccal samples (where available) will be subjected to DNA/RNA extraction for tumour and germline sequencing, respectively. The samples will be provided to collaborators at the University of Melbourne Centre for Cancer Research (UMCCR) for whole genome and transcriptome sequencing. Bioinformatic analysis will be performed by collaborators at UMCCR and the Walter and Eliza Hall Institute of Medical Research (WEHI) for bioinformatic analysis to determine the relationship between the events.

4. Study Parameters and Data Management

The following results will be collected:

Genomic sequencing and pathology data will be stored indefinitely in secure databases at University of Melbourne or on external cloud-based servers under control of the study investigators. The data obtained from this study may be used for future ethically approved research studies, with prior approval by the principal investigators of this study and HREC.

Study participants’ confidentiality and privacy will be maintained. Data including identifying details, minimal clinical history, clinical follow up data and sequencing results will be stored in a password protected database with restricted access. All documents and study data will be stored electronically on the study-specific password-protected database/electronic folders. Only necessary study-related personnel will have password access. All study-related personnel are bound by professional standards of participant information confidentiality and will work to protect participant confidentiality at all times.

5. Outcomes and significance

Findings from this work will directly complement the PROSPECT study. It should reveal the nature of recurrences (*de novo* tumours versus a refractory tumour recurrence).

PAM50 analysis of the index lesion will determine if the PAM50 subtype was unfavourable (e.g. Luminal B) and/or the Risk of Recurrence Score was high. This could have potential utility as an adjunctive test for predicting relapse for patients in this study and therefore could inform future follow up study (or retrospective analysis of additional index tumours).
